11. DESCRIPTION OF ASSESSMENTS

11.1. Safety Assessments

Safety will be assessed from physical examination, AE reporting, standard and orthostatic vital signs (BP, RR, and HR), clinical laboratory values (hematology and biochemistry), ECGs, and spirometry and DLco for evaluation of pulmonary function. In addition, UPDRS Part 4, and evaluations for assessing suicidality, somnolence, and impulse control disorders will be done.

11.1.1. Physical Examination

A complete physical examination (head, eyes, ears, nose, and throat [HEENT], heart, lungs, abdomen, skin, cervical and axillary lymph nodes, neurological, and musculoskeletal systems) will be performed at the visits specified in [Appendix 2](#) through [Appendix 15](#). Genital, rectal, and breast examination may be excluded if not clinically indicated. Height (cm) and weight (kg) will be assessed at screening by qualified personnel. Physical examinations will be performed by a

physician. In addition, medical history will be recorded at screening, including smoking history, if applicable.

A brief physical exam to verify continued patient eligibility and to follow up any change in medical history will be performed at visits specified in [Appendix 2](#) through [Appendix 15](#). Symptom-driven brief physical examinations will be performed as clinically indicated at any study visit. All changes identified as clinically noteworthy must be recorded as AEs.

11.1.2. Vital Signs

Standard Vital Signs

Vital sign measurements will include RR, BP (systolic [SBP] and diastolic [DBP]), and HR after the patient has rested in a supine or semi-supine position for at least 5 minutes.

Blood pressure must be assessed using an appropriate device, and the arm position must be standardized for each patient using a cuff size that is appropriate for the patient. These measurements are to be taken in the same arm for the duration of the study. The position of the cuff on the arm should be in line with the heart with the arm lying next to the patient when semi-supine and should be in line with the heart at approximately a 45-degree angle from horizontal for the standing measurements. “Standard” BP and HR measurements should be taken after resting in a supine or semi-supine position for at least 5 minutes.

Respiratory rate should be recorded for 30 seconds, and the value multiplied by 2 for the rate per minute.

Vital sign measurements will be repeated if clinically significant or machine/equipment errors occur. If out-of-range BP, RR, or HR results are observed, the assessments may be repeated at the investigator’s discretion. Any confirmed, clinically significant vital sign measurements must be recorded as AEs.

Orthostatic Vital Signs

At screening (SV1 or SV2) and at each subsequent study visit and in the event of a clinically significant finding that could be suggestive of symptomatic orthostatic hypotension (e.g., dizziness, lightheadedness, or other AE), orthostatic vital signs will be performed. During the orthostatic vital signs assessment, at least one other staff member familiar with the study (not measuring vital signs) must be present should symptoms or an AE occur.

In order to obtain orthostatic vital signs, patients should undergo the following procedures in sequential order:

1. After the supine/semi-supine BP and HR measurements have been done, the patient will be asked to sit on the edge of the bed/table with feet on the floor (or with feet dangling from the bed/tableside depending on the height of the bed/table) for approximately 30 seconds.
2. The person performing the assessment will then ask the question, “Are you ready to stand?”
 - If the patient responds in the affirmative, the patient will proceed to stand and then be asked to remain standing for 2 minutes. After standing for 2 minutes, BP and HR will be recorded.

- If the patient states that he or she is not ready to stand, the patient will be allowed to sit as positioned for 1 additional minute and will be asked again if they are ready to stand. The patient will proceed to stand. After standing for 2 minutes, one measurement will be taken for BP and HR.
- If the individual is still unable to stand, vital signs will be measured while the patient is in an upright seated position.

Orthostatic hypotension will be defined as a reduction in SBP of 20 mmHg or more, and/or a reduction in DBP of 10 mmHg or more, for the standing measurement compared to the semi-supine measurement. If orthostatic hypotension is suspected, the measurement process may be repeated at the investigator's discretion. Any changes of potential clinical concern will be recorded as AEs.

11.1.3. Electrocardiogram

Standard 12-lead ECGs will be obtained after the patient has rested in a supine position for at least 5 minutes. Electrocardiograms will be measured using an ECG machine that automatically calculates the HR and measures PR, QRS, QT, QT interval corrected using Bazett's formula (QTcB) and QT interval corrected using Fridericia's formula (QTcF).

Please refer to [Appendix 2](#) through [Appendix 15](#) regarding specific times of ECG assessments at individual study visits.

Electrocardiogram equipment will be provided to each study site to perform all assessments.

Electrocardiograms will be repeated if clinically significant abnormalities are observed or artifacts are present. Electrocardiograms will be reviewed by qualified staff and over-read by the Central ECG Laboratory.

11.1.4. Laboratory Parameters

Hematology, clinical chemistry, and additional laboratory parameters to be tested are listed in [Appendix 17](#). Patients do not need to be in a fasted state at the time of any laboratory sample; however, fasted status will be documented (with fasting defined as at least 4 hours following the last meal or snack).

Laboratory samples will be analyzed by a central laboratory (ACM Global Central Laboratory) to ensure consistent interpretation of results. In the event of an unexplained clinically significant abnormal laboratory test value, the test should be repeated immediately and followed up until it has returned to the normal range and/or an adequate explanation of the abnormality is found.

11.1.5. Pregnancy Status

Women of child-bearing potential must have a negative pregnancy test (serum hCG test) at screening. A serum hCG test will be performed at screening (SV1 or SV2) and at TV/OV1, TV/OV3, TV/OV4, TV/OV5, and TV/OV6, if applicable.

If sexually active and the female is of child-bearing potential, the patient (and his/her partner) should use adequate contraceptive measures for the duration of the study. Adequate measures should consist of 2 forms of contraception (except in cases of surgical sterilization), at least 1 of which must be a barrier method (e.g., male partner uses condoms, plus female partner uses

diaphragm and spermicidal gel, or cervical cap and spermicidal gel, or intrauterine device, or oral contraceptive pill).

Female patients found to be pregnant will be withdrawn from further treatment, but will be followed for the duration of their pregnancy.

11.1.6. Spirometry

The following is a description of the pulmonary function testing at clinical sites:

Pulmonary function will be measured by spirometry using the guideline specified by the Third National Health and Nutrition Examination Survey (NHANES III) ([Hankinson 1999](#)). Spirometry (with the exception of spirometry being performed in conjunction with DLco) will be performed by trained and qualified staff at each study site. Spirometry data will be reviewed by a central spirometry laboratory (Biomedical Systems, Inc.) which will provide a quality over-read of all evaluations based on acceptability and repeatability metrics in accordance with ATS criteria ([Miller et al., 2005](#)). FEV₁, FVC and FEV₁/FVC ratio will be recorded from the single “best test” (based on effort with highest summed FEV₁ and FVC). Variables and comparisons will include the actual and expected forced FEV₁, FVC, and FEV₁/FVC ratio. Patients with FEV₁ <50% of predicted for race, age, sex, and height, or FEV₁/FVC ratio ≤60% in the ON state at screening will be excluded from the study. A pulmonologist will review the spirometry tracings/morphology of any patient with an FEV₁ that is ≥50% to <60% of predicted or an FEV₁/FVC ratio that is >60% to <70% at screening in order to determine eligibility. All patients with an FEV₁/FVC ratio that is >60% to <70% at screening will complete spirometry before and after the administration of a bronchodilator in a pulmonary function laboratory. Testing will be performed in accordance with the 2005 ATS/ERS criteria. The results of the bronchodilator challenge will be reviewed by a pulmonologist. Any subject requiring pulmonary adjudication at screening will not be randomized until after full pulmonologist review and approval.

Spirometry assessments will be done at the time points indicated in [Appendix 2](#) through [Appendix 15](#). The patient’s motor state at the time of each spirometry assessment will be recorded. At SV1, spirometry assessments should be done while the patient is in both the ON and OFF states. At SV2, spirometry assessments will be done only if a repeat measurement is needed for assessing eligibility.

Spirometry equipment will be provided to each study site to perform all spirometry assessments.

11.1.7. Carbon Monoxide Diffusing Capacity

Patients will undergo diffusing capacity of the lungs for carbon monoxide (DLco) assessments, which will be performed in accordance with ATS criteria ([Miller et al., 2005](#)), at a dedicated pulmonary function facility after SV2 (and prior to TV/OV1), within 2 weeks prior to TV/OV3, TV/OV4, TV/OV5, and TV/OV6, and at 4 to 5 weeks after TV/OV6, as described in the [Appendix 2](#) through [Appendix 15](#). These assessments should be performed while the patient is in the ON state (as reported by the patient to the pulmonary technician). Trained and qualified pulmonary function facility technicians will perform a slow vital capacity maneuver, followed by DLco, and then spirometry.

DLco and slow vital capacity maneuvers will be assessed and processed in accordance with ATS/ERS standards. Spirometry procedures will be conducted at the same visits in the same manner as those conducted at clinical sites in accordance with ATS criteria (see [Section 11.1.6](#)). All DLco data collected at pulmonary function labs will be sent to and reviewed by a central Pulmonary Function Testing reviewer (TechEd Consultants).

11.1.8. Adverse Events

An AE is any symptom, physical sign, syndrome, or disease that either emerges during the study or, if present at the start of the study, worsens during the study, regardless of the suspected cause of the event. Changes in conditions present at screening and new symptoms, physical signs, syndromes, or diseases should be noted on the AE page of the eCRF during the study. Any AEs reported prior to the first study treatment (or TV/OV1) will be considered baseline AEs, and AEs reported from first treatment (or TV/OV1) will be considered treatment-emergent adverse events (TEAEs).

AEs may be volunteered spontaneously by the patient, discovered as a result of general questioning by the study staff, or determined by physical examination. At each visit, the patient will be asked, “Have you experienced any problems since your last visit?” All AEs will be recorded on the eCRF. For all AEs, the investigator must pursue and obtain information adequate both to determine the outcome of the AE and to assess whether it meets the criteria for classification as a serious AE requiring immediate notification. Follow-up of the AE, even after the date of therapy discontinuation, is required if the AE persists until the event resolves or stabilizes at a level acceptable to the investigator.

In order to avoid vague, ambiguous, or colloquial expressions, all AEs should be recorded in standard medical terminology rather than the patient’s own words. Each AE will also be described in terms of duration, frequency, intensity, association with the study medication, assessment of possible causes, actions taken, and outcome, using choices given on the eCRF. Specific guidelines for classifying AEs by intensity and relationship to study medication are given in [Table 3](#) and [Table 4](#), respectively.

Table 3 Classification of Adverse Events by Intensity

MILD: An event that is easily tolerated by the patient, causing minimal discomfort and not interfering with everyday activities.

MODERATE: An event that is sufficiently discomforting to interfere with normal everyday activities.

SEVERE: An event that prevents normal everyday activities.

Table 4 Classification of Adverse Events by Relationship to Study Medication

Definitely not related: The AE is definitely not related to the drug. This designation should be reserved for those events which occur prior to study treatment or for those events which cannot be even remotely related to study participation (e.g., injuries sustained in an automobile accident as a passenger).

Unlikely related: There is no reasonable association between the study treatment and the suspected event and the event could have been produced by the patient's clinical state or other modes of therapy administered to the patient.

Possibly related: The suspected adverse event may or may not follow a reasonable temporal sequence from study treatment administration but seems to be the type of reaction that cannot be dismissed as unlikely. The event could have been produced or mimicked by the patient's clinical state or by other modes of therapy concomitantly administered to the patient.

Probably related: The suspected adverse event follows a reasonable temporal sequence from study treatment administration, abates upon discontinuation of the treatment, and cannot be reasonably explained by the known characteristics of the patient's clinical state.

Definitely related: This designation should be reserved for those events which have no uncertainty in their relationship to treatment administration.

When changes in the intensity of an AE occur more frequently than once a day, the maximum intensity for the experience should be noted. If the intensity category changes over a number of days, then those changes should be recorded separately (with distinct onset dates).

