10.3.2. Treatment Visit/Observational Visit 1 (at least 7 days after SV2)

10.3.2.1. Treatment Visit 1 for the CVT-301 Treatment Group

Patients will complete the Screening ON/OFF Episodes Log and PD Diary for the 3 consecutive days prior to TV1.

Patients will report to the clinic after having taken their usual PD medications prior to the visit. The timing of arrival for TV1 should be scheduled to increase the likelihood that patients will be in the ON state upon arrival (i.e., they should arrive to the clinic as shortly as feasible after taking their standard oral PD medications at home). Patients will bring to the clinic all of their usual prescribed PD medications.

On Arrival to the Clinic

The following list is a suggested schedule for this visit:

- Collect, review, sign, and date the PD Diary and Screening ON/OFF Episodes Log and document whether these were completed correctly.
- Confirm that the DLco assessment has been performed. If the DLco assessment has not been completed prior to the visit, the study visit must be re-scheduled.
- Record the time that patients took their usual PD medications prior to the visit.
- Record any changes in the usual PD medication dose/regimen.
- Record all concomitant medications.
- Perform the PDQ-39 in an ON state.
- Perform a brief physical examination.
- Patients will complete the UPDRS Part 2 and S&E ADL scales (preferably in the ON state).
- Patients will complete the UPDRS Part 4 (Questions 32-35 and 36-39).
- Perform a 12-lead ECG.
- Record standard and orthostatic BP and HR. Record RR.
- Perform spirometry (preferably performed in the ON state; record the patient's motor state on the spirometry source record).
- Collect blood for clinical laboratory tests including serum pregnancy test, if applicable. Document fasting status.
- Perform the baseline assessments using the C-SSRS, Epworth Sleepiness Scale, and the QUIP.
- Distribute the PD Diary and review instructions for completion for recording time asleep, time OFF, time ON without dyskinesia, time ON with non-troublesome

dyskinesia, and time ON with troublesome dyskinesia (to be completed for the 3 consecutive days prior to TV2, TV3, TV4, TV5, and TV/6).

- Distribute the Inhaled Dosing Log and review instructions for completion for recording the number of times the inhaler was used and the number of capsules used for each inhalation treatment (to be completed daily throughout the 12-month treatment period).

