- Distribute study drug kits to patients. Instruct patients to collect used empty capsules and return them at the next visit along with the PD Diary, Inhaled Dosing Log, and other study supplies.
- Re-train patients on the proper use of the inhaler with sham capsules, including a review of the IFU.

Study Drug Dosing

Immediately pre-dose, perform a spirometry assessment (record the patient's ON/OFF state on the spirometry source record). Under clinic staff supervision, preferably between 2 and 5 hours after receiving their standard dose of PD medication (in the OFF state), patients will prepare and self-administer their first dose of study drug from the study drug kits provided (i.e., 2 capsule inhalations of CVT-301). Patients will be permitted sips of water between capsule inhalations as needed. The dosing time is defined to be when the patient's OFF state is recognized by both the patient and investigator to be at a level similar to the investigator-confirmed severity experienced at SV1 and preferably between 2 and 5 hours after their prior oral PD medication.

Note: Instructions for how to properly use the CVT-301 system are outlined in the Instructions for Use document that is included with every CVT-301 study kit. Refer to [Appendix 21](#) for additional system information.

Post-dose (10 – 60 minutes)

The following post-dose safety evaluations will be performed:

- Record vital signs (standard and orthostatic BP and HR) at 20 and 60 minutes post-dose.
- Record RR at 10, 20, 30, and 60 minutes post-dose.
- Monitor for AEs throughout the visit.

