10.3.2.2. Observational Visit 1 for the Observational Cohort

Patients will complete the Screening ON/OFF Episodes Log and PD Diary for the 3 consecutive days prior to OV1.

Patients will report to the clinic after having taken their usual PD medications prior to the visit. The timing of arrival for OV1 should be scheduled to increase the likelihood that patients will be in the ON state upon arrival (i.e., they should arrive to the clinic as shortly as feasible after taking their standard oral PD medications at home). Patients will bring to the clinic all of their usual PD medications.

On Arrival to the Clinic

The following list is a suggested schedule for this visit:

- Collect, review, sign, and date the PD Diary and Screening ON/OFF Episodes Log and document whether these were completed correctly.
- Confirm that the DLco assessment has been performed. If the DLco assessment has not been completed prior to the visit, the study visit must be re-scheduled.
- Record any changes in the usual PD medication dose/regimen.
- Record all concomitant medications.
- Perform the PDQ-39 in an ON state
- Perform a brief physical examination.
- Patients will complete the UPDRS Part 2 and S&E ADL scales (preferably in the ON state).
- Record standard and orthostatic BP and HR. Record RR.
- Perform a 12-lead ECG.
- Perform spirometry (preferably performed in the ON state; record the patient's motor state on the spirometry source record).
- Collect blood for clinical laboratory tests including serum pregnancy test, if applicable. Document fasting status.
- Perform the baseline assessments using the C-SSRS, Epworth Sleepiness Scale, and the QUIP.
- Monitor for AEs.

The next visit will be scheduled and the patient will be discharged from the visit.

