12.5. Safety Analysis

The disposition of the patients will be summarized by tabulating the number of screened, randomized, completed, and discontinued patients. The reasons for premature discontinuations will be tabulated.

The extent of exposure to study treatment will be summarized for the patients who received CVT-301 treatment. The time period between TV/OV1 and TV/OV6 (or Early Withdrawal Visit) will be used as the measure of extent of exposure for the patients randomized to the observational cohort. Adverse events will be tabulated by treatment group according to the Medical Dictionary for Regulatory Activities (MedDRA). Study-emergent and treatment-emergent adverse events (TEAEs) will be summarized by body system and preferred term. For patients in the observational cohort, the AEs collected between TV/OV1 and TV/OV6 (or Early Withdrawal Visit) will be considered as TEAEs. Furthermore, the time of onset of the TEAEs will be summarized.

For vital signs, ECG parameters, spirometry measurements, and DLco, the changes from pre-dose to post-dose assessments of the corresponding day will be calculated and described using descriptive statistics. For spirometry, DLco, and safety laboratory variables, the differences in pre-dose values between the study days will be described. Furthermore, the changes in the spirometry values and difference between the groups will be estimated using a Mixed Model for Repeated Measurements (MMRM) similar to the one used for the efficacy variables. The proportion of patients with abnormal spirometry values will be tabulated using different criteria for the threshold (e.g., at least 10% or 20% change from baseline at any single visit, at least 10% or 20% change from baseline on at least 2 consecutive visits). The proportions of patients meeting ATS quality criteria (and also for those 'rejected') will be summarized. All spirometry analyses will be performed both for all patients regardless of the ATS quality criteria and separately excluding the assessments not meeting the ATS quality criteria.

At least the following variables will be analyzed:

- Vital signs: standard and orthostatic systolic and diastolic BP and HR.
- ECG: HR, PR, QRS, QT and RR intervals, QTcB (Bazett's correction formula calculated as $QT/RR^{1/2}$) and QTcF (Fridericia's correction formula calculated as

QT/RR^{1/3}). ECG parameter values or parameter changes of potential clinical concern will be tabulated.

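### Treatment-emergent adverse events are defined by when they are reported or collected, not by onset or worsening, so events that began in screening can be tabulated as treatment-emergent

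*Protocol*

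**What the plan says.** Section 11.1.8 fixes both sides of the cut by date of report. Before it: "Any AEs reported prior to the first study treatment (or TV/OV1) will be considered baseline AEs". After it: "AEs reported from first treatment (or TV/OV1) will be considered treatment-emergent adverse events (TEAEs" in the protocol's abbreviation. The parenthesis naming TV/OV1 is not assigned to either arm there.

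Section 12.5, repeated in the synopsis, gives a rule for one arm only: "For patients in the observational cohort, the AEs collected between TV/OV1 and TV/OV6 (or Early Withdrawal Visit) will be considered as TEAEs". No equivalent window is given there for CVT-301 patients.

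The AE enquiry looks backwards. At every visit the patient is asked: "Have you experienced any problems since your last visit". Visit 1 takes place "at least 7 days after SV2" (Section 10.3.2).

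For AE collection at visit 1, the OV1 list has "Monitor for AEs" (Section 10.3.2.2). The TV1 list has "Monitor for AEs throughout the visit" (Section 10.3.2.1), placed among the post-dose items.

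On intensity, Section 11.1.8 adds: "If the intensity category changes over a number of days, then those changes should be recorded separately (with distinct onset dates" in brackets.

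**The concern.** A treatment-emergent event should be one that starts, or gets worse, once treatment or the observation period has begun. A report-date rule with a look-back question does not deliver that. At visit 1 the question reaches back over at least 7 days of screening, and anything first mentioned on the wrong side of the cut carries the wrong label. The wording about emerging or worsening appears only in the general definition of an AE, where it is relative to the study and not to treatment. Time of onset is summarized in Section 12.5, but only for events already classed as TEAEs.

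The rule also sits badly with Table 4, which reserves its lowest relatedness category partly for events occurring before study treatment. One event could be definitely unrelated because it came before treatment and still be counted as treatment-emergent.

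AE reports serve a secondary objective (Section 6) and are tabulated by treatment group (Section 12.5). What is at stake is whether those TEAE tables describe the on-study period in each arm, and whether the columns can be read side by side.

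**Working it through.** The plan states no figure that depends on this definition, so the check applies the stated rule to one case: **an AE with onset between SV2 and visit 1 that does not worsen afterwards**. Section 9.4.1 requires illnesses arising from consent onward to be documented as AEs, so such an event is recorded. What varies is when it is first told.

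| First told | Observational cohort | CVT-301 |
|---|---|---|
| To the site before visit 1 | Baseline | Baseline |
| At the start of visit 1 | TEAE (reported from OV1 on) | Baseline (before first dose) |
| Later in visit 1, after the dose | Not applicable | TEAE |
| Call 1 to 3 days after TV1 | No such call | TEAE |
| Call about 2 weeks before visit 2, or at visit 2 | TEAE | TEAE |

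Under an onset-or-worsening rule every cell becomes baseline.

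The second row depends on the reading:

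1. **Cut is OV1 for controls and first dose for CVT-301.** Section 12.5 supports this by tying the TV/OV1 window to the observational cohort. The dose at TV1 is given in the OFF state, after the arrival assessments, so there is time within TV1 for a pre-dose report. The arms then differ for the same event.
2. **Cut is TV/OV1 for both arms.** Section 11.1.8 does not rule this out. The second row becomes TEAE in both arms. The asymmetry goes, but the misclassification stays and widens.
3. **The Section 12.5 window excludes reports made at OV1 itself.** Its wording does not say. Sections 11.1.8 and 12.5 would then disagree about OV1 reports.

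The last row is misclassified in both arms on every reading, and so are the two rows for reports made after the dose in the CVT-301 arm.

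**Direction and size.** Let *p* be the true proportion of patients with a TEAE, equal in both arms. Let *q_C* and *q_T* be the proportions of control and CVT-301 patients with a mislabelled screening event, independent of true TEAEs. All three are assumptions, because the protocol gives no AE rates.

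- Apparent proportion in an arm = 1 − (1 − *p*)(1 − *q*)
- Apparent difference, CVT-301 minus control = (1 − *p*)(*q_T* − *q_C*)

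With *p* = 50%:

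- *q_C* = 10%, *q_T* = 0: 0.5 × (0 − 0.10) = −5.0 points (0.05 × 115 = 5.75, about 6 of 115 controls)
- *q_C* = *q_T* = 10%: 0
- *q_C* = 5%, *q_T* = 10%: 0.5 × 0.05 = +2.5 points

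If *q_T* is set to 0, *p* from 30% to 70% and *q_C* from 5% to 20% give −1.5 points (0.3 × 0.05) to −14 points (0.7 × 0.20). Swapping the two arms' values reverses the sign. The sign depends only on which of *q_T* and *q_C* is larger, and the protocol does not settle that.

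**The case against.** The strongest reply is that this is a matter of wording. Section 12 says the SAP gives the detailed technical description and supersedes the protocol where they differ. No between-arm test of AEs is planned, and the between-group objective concerns pulmonary safety measures. The primary objective, based on spirometry, is unaffected. All of that stands and limits the weight of the point. It does not remove it, because the protocol does not leave the TEAE rule open. It states one, in three places, and that rule gives the wrong label when followed.

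Three stronger readings are tempting but not supported.

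- **That pre-baseline events are added to the control column only, making CVT-301 look safer.** The TV1 arrival list has no AE item, and AE monitoring runs through the whole visit, so a screening event may well be told after the dose and become a TEAE. Only CVT-301 patients receive the call 1 to 3 days after TV1, which Section 10.3.2.1 says is partly to monitor for AEs. That extra contact can bring late-told screening events into the CVT-301 column.
- **That the length of the screening interval, as a share of follow-up, measures the effect.** It measures calendar time, not events. Patients are also called 4 to 6 days before visit 1 and told to contact the site about an intervening illness, especially respiratory. Illnesses told then are baseline in both arms.
- **That separate records for intensity changes inflate event counts.** That is a recording rule for the eCRF and applies equally to both arms. How records are collapsed and counted is ordinary SAP content.

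**Conclusion.** The point holds as a fault in the stated definition. Sections 11.1.8 and 12.5 and the synopsis class AEs by report or collection date. Combined with a look-back question at every visit, this labels some screening-onset events as treatment-emergent. That conclusion needs no assumption beyond patients sometimes mentioning such an event late.

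The difference between arms for an event told at the start of visit 1 holds on the more natural reading, in which the TV/OV1 cut belongs to the observational cohort. It is not the only possible reading.

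The net direction and size of any bias cannot be determined from the protocol. The percentages worked above rest on assumed rates and show only that the sign can go either way. The consequence is confined to the descriptive TEAE tables.

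**What to change.** In Section 11.1.8, Section 12.5 and the synopsis, replace the report- and collection-date wording with one rule: a TEAE is an AE whose onset, or whose worsening over its pre-treatment intensity, falls at or after the first dose (CVT-301) or after completion of the OV1 assessments (observational cohort), whatever the date on which it is reported. Add that a fall in intensity of a pre-existing event is not a new TEAE. The existing end of the control window can stay.

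The cost is a few sentences in three places and the matching derivation in the analysis programs. No assessment or visit is added: the protocol already asks for distinct onset dates when intensity changes and plans to summarize time of onset, so the dates should be available. For events starting on the day of TV1, the eCRF needs to show whether onset was before or after the dose. If the SAP already defines TEAEs by onset, only the protocol text needs to be brought into line.
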